### 16.2 Multiple Hypothesis Testing Adjustment for CoP Analysis

For the univariable CoP analyses of the prioritized set of Day 57 antibody markers among the five specified marker variables, the analysis plan seeks evidence of a CoP through four different causal effect approaches. Because of this looking for evidence through different lenses, for CoP analysis we do not focus on family-wise error rate adjustment, because FWER-adjustment aims to control the risk of making even a single false rejection. Rather, in an effort to build a body of consistent evidence and to ensure that a large fraction of that evidence is reliable, for CoP analysis we focus on false discovery rate correction. To do this, we use the same permutation-based method (Westfall et al., 1993) that is used for CoR analysis. The multiplicity adjustment is performed across the Day 57 markers and across the set of CoP methods that are applied, in a single suite of hypothesis tests with calculation of q-values. As a guideline for interpreting CoP findings (but not meant to be a rigid gateway), markers with unadjusted p-value  $\leq 0.05$  and q-value  $\leq 0.10$  are flagged as having statistical evidence for being a CoP.

# 17 CoP: Meta-Analysis Analysis Plan

We provide a brief summary of the overall plan, where the details will be developed closer to the time that data are available for meta-analysis of multiple phase 3 vaccine efficacy trials.

Once data sets are available from the set of USG COVID-19 Response Team phase 3 trials, the data sets will be combined for additional analyses to support development of immune CoPs. Data analysis of the combined data sets provides interpretable results based on the standardization of the USG COVID-19 Response Team phase 3 trial protocols – including harmonized study endpoints, follow-up, and blood storage time points – and on the common statistical analysis plan and laboratories/immunoassays (where the use of the Duke pseudovirus assay in some USG COVID-19 Response Team trials and the Monogram pseudovirus assay in other USG COVID-19 Response Team trials implies that the statistical analysis will make use of concordance testing data for making results interpretabile referenced to one of the assays.) Meta-analysis surrogate endpoint evaluation methods will be applied to the combined data sets, both for assessing Day 29 and Day 57 antibody markers (Stage 1) as surrogate endpoints for COVID and for secondary outcomes, and for assessing the antibody markers over time (Stage 2) as surrogate endpoints for COVID and for secondary outcomes.

Both individual-level and trial-level meta-analysis will be applied, where the latter studies the association of vaccine effects on an antibody marker with vaccine effects on a study outcome, for example assessing how GMT nAb cID80 titer associates with the level of vaccine efficacy against COVID. Meta-analysis has a special role in being the only correlates approach that can potentially assess immunologic markers as CoPs that are measured using sampling types that were not stored from most trial participants (e.g., PBMC for measuring T cell responses). While the current statistical analysis plan focuses on assessing antibody markers as correlates, in the future plans may be devised to incorporate T cell response data (and potentially other data types) from phase 1-2 studies into meta-analysis evaluation.

In addition to applying formal meta-analysis surrogate endpoint evaluation methods, some of the CoR and CoP statistical methods applied to the individual phase 3 trial data sets will be adapted for application to the combined data sets. This will allow addressing the following objectives: (1) to assess consistency of CoRs and CoPs across trials, subpopulations, and vaccine platforms; (2) to evaluate how well an antibody marker CoR for an outcome developed in one phase 3 trial predicts the same outcome in the other phase 3 trials (cross-validation prediction accuracy); and (3) to provide data for prediction modeling of what would be the efficacy of a new vaccine based on its distribution of antibody markers. Objective (2) provides some empirical data for considering appropriateness of use of a CoP across vaccine platforms.

We will consider two meta-analytic statistical frameworks for evaluating candidate surrogate endpoints: (1) Gabriel et al. (2016, 2019) "generalized surrogate" approach and (2) Molenberghs et al. (2000, 2007) meta-analytic approach.

### 17.1 Method of Gabriel et al. (2016, 2019)

Gabriel et al. (2016, 2019) describe a non-parametric Bayesian hierarchical framework for the modeling of vaccine efficacy and one or more potential surrogate endpoint markers. The framework enables evaluation of a triallevel general surrogate (TLGS): the ability to predict the efficacy of a vaccine based on trial-level observations of a surrogate marker distribution. The model does not require individual-level data as input; instead, the effects of the vaccine on the true endpoint (i.e. vaccine efficacy) and on the surrogate endpoint (i.e. a vaccine-induced immune response) are modeled from each observed randomized trial using a bivariate normal distribution. From the Bayesian posterior it is then possible to predict the vaccine efficacy (with 95% credible interval) in a new setting based on the observed distribution of the surrogate marker. In concept the model is similar to that of locally weighted linear regression (LOESS). With this framework it is possible to evaluate the strength of surrogacy using absolute prediction error, compare multiple candidate surrogates based on relative prediction error and predict vaccine efficacy in a new setting.

The Gabriel et al. framework is implemented in R using code adapted from their publication (https://github.com/sachsmc/DPpackagemod; 2019). We will use the estimates of vaccine efficacy and candidate surrogate marker distributions from all available Phase 3 randomized, placebo controlled trials; inclusion will be contingent on normalization of the surrogate marker to the WHO or some other human convalescent serum (HCS) standard. Performance will be measured as the absolute difference between the predicted and observed vaccine efficacy (on the log relative-risk scale) with the mean taken across trials in a leave-one-out cross-validation framework (i.e. the efficacy for trial A is predicted based on the surrogate marker in trial A and the efficacy and marker distributions in the other trials). An example analysis is provided using the ratio of the virus neutralization titer in vaccine recipients to human convalescent sera (HCS) as the surrogate marker (Figure 5); a similar analysis was also performed using the ratio of the binding IgG antibody (ELISA) to the same measure in HCS (Figure 6). In the example, vaccine efficacy was estimated from Phase 3 trials while the central value of the marker distribution were estimated (mean and 95% confidence interval) from Phase 1/2 trials in comparable populations. Details of the data sources are available in Earle at al. (2021).

### 17.2 Method of Molenberghs et al.

Buyse, Molenberghs et al. originally proposed a meta-analytic framework for evaluating a surrogate endpoint by building on Prentice's (1989) surrogacy criteria and generalizing to a multi-trial setting. Similar to the Prentice criteria, the approach is based on a system of three linear regressions of: (i) the treatment effect on the true endpoint, (ii) the treatment effect on the surrogate endpoint and (iii) the association of the surrogate endpoint with the true endpoint. This model is expanded to a multi-trial setting, each potentially with a distinct treatment (i.e. vaccine). Unlike Gabriel et al. (2016, 2019), the model is fit using individual-level data; the fitted parameters of the model enable assessment of the strength of a surrogate endpoint for each trial as well as overall. Originally they proposed a metric of surrogacy called the relative effect (RE), which was the ratio of the regression coefficient indicating the treatment effect on the true endpoint divided by that of the treatment effect on the surrogate. The relative effect indicates the extent to which the treatment effect on the true endpoint can be predicted by measuring the treatment effect on the surrogate.

In more recent work, Alonso and Molenberghs (2007) used information theory and developed a similar metric,  $R_h^2$ , which generalizes to settings with nonnormal true and surrogate endpoints. The information theoretical framework is helpful because it provides an intuitive framing of the issue of surrogate marker validation: we want to gain information about the unobserved treatment effect on the true endpoint using the known treatment effect on the surrogate. The  $R_h^2$  metric is similar to RE in that when  $R_h^2 \approx 1$  the potential surrogate is promising and the interpretation is that once the surrogate is known, almost all of our uncertainty about the true endpoint is gone. The information-theoretic Molenberghs et al. approach is implemented in their R package *surrogate*. The analysis takes as input the individual-level data for multiple trials, including the true and surrogate endpoints. Like implementation of the Gabriel at al. framework, inclusion of trials will be contingent on normalization of the surrogate markers to the WHO International Units. The output of the analysis will be estimates of the parameter  $R_h^2$  for each trial and overall including a point-estimate and 95% confidence interval.

# 18 Estimating a Threshold of Protection Based on an Established or Putative CoP (Population-Based CoP)

For each antibody marker studied as a CoP, we will apply the Chang-Kohberger (2003) / Siber (2007) method to estimate a threshold of the antibody marker associated with the estimate of overall vaccine efficacy observed in the trial.

This method makes two simplifying assumptions: (1) that a high enough antibody marker value  $s^*$  implies that individuals with  $S > s^*$  have essentially zero disease risk (perfect protection) regardless of whether they were vaccinated; and (2)  $P(Y = 1|S \leq s^*, A = 1)/P(Y = 1|S \leq s^*, A = 0) = 1$  (zero vaccine efficacy if  $S \leq s^*$ ). Based on these assumptions,  $s^*$  is calculated as the value equating  $1 - \hat{P}(S \leq s^*|A = 1)/\hat{P}(S \leq s^*|A = 0)$  to the estimate of overall vaccine efficacy. This estimate is supplemented by estimating the reverse cumulative distribution function (RCDF) of S in baseline negative vaccine recipients and calculating a 95% confidence interval for the threshold value  $s^*$  as the points of intersection of the estimated RCDF curve with the 95% confidence interval for overall vaccine efficacy (as in the figure in Andrews and Goldblatt, 2014).

This method essentially assumes that S has already been established as a CoP, and under that assumption estimates a threshold that may be considered as a benchmark / study endpoint for future immunogenicity vaccine trial applications.

It is acknowledged that this approach makes highly simplified assumptions; nonetheless it may yield a useful benchmark and complementary information

on a threshold correlate of protection.

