#### 6 Timeline/Sequencing of Correlates Analyses

The correlates analyses are initiated by the availability of (a) a data set defined at or after the primary analysis data set triggered by the accrual of a certain number of primary endpoints (typically approximately 150 in U.S. phase 3 studies); and (b) Day 1, 57 antibody marker data from correlateseligible COVID primary endpoint cases from at least 25 baseline negative vaccine recipients. The latter requirement ensures that there are enough endpoint cases to achieve worthwhile precision for CoR analyses. The HVTN 505 trial serves as a precedent where 25 evaluable vaccine recipient cases provided enough data to reasonably characterize correlates of risk for a preventive candidate HIV vaccine (Janes et al., 2017; Fong et al., 2018; Neidich et al., 2019; Gilbert et al., 2020b). In addition, simulation studies show that correlates analyses at 20 endpoints have notably lower precision.

Table 4 shows the minimum number of baseline negative vaccine recipient endpoints evaluable for correlates analyses that are required before conducting the various planned correlates analyses.

Correlates Analysis Type	Number
CoRs (Risk Prediction Modeling)	
a. (Semi)parametric models with strongly parametrized associations:	
Cox, hinge/threshold logistic regression	25
b. Flexible parametric models: Generalized additive model	35
c. Nonparametric thresholds: Donovan et al. $(2019)/$	
van der Laan et al. (2020)	35
d. Superlearner estimated optimal surrogate	35
CoP: Correlates of VE	50
CoP: Controlled VE	50
CoP: Stochastic Interventional VE	50
CoP: Mediators of VE	50

Table 4: Minimum Numbers of Evaluable Endpoints in Baseline Negative Vaccine Recipients toInitiate Correlates Analyses

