#### 8.1 Prototype USG COVID-19 Response Team immunogenicity subcohort

Table 5 summarizes the size of the prototype USG COVID-19 Response Team immunogenicity subcohort, by baseline factors used to stratify the random sampling. In this subcohort 6 baseline demographic strata are used; if a trial has a different number of baseline demographic strata, then the table would be modified, holding the total sample size of the subcohort approximately fixed. For U.S. strata, all USG COVID-19 Response Team trials specify 50:50 balance by underrepresented minority status Yes:No. The subcohort sampling is implemented to create representative sampling across the entire period of enrollment. Non-USG COVID-19 Response Team trial sampling designs would likely be similar, with different baseline sampling strata perhaps even the simplest case with no sampling strata and use of simple random sampling. 'At-risk' refers to participants considered to be at heightened risk of severe COVID-19 illness based on a specified list of conditions.
Table 5: Planned Immunogenicity Subcohort Sample Sizes by Baseline Strata for Antibody Marker Measurement

	Baseline SARS-CoV-2 Negative 							Baseline SARS-CoV-2 $Positive^3$					
Bas. Cov. Strata 	1	2	3	4	5	6	1	2	3	4	5	6	
Vaccine	150	150	150	150	150	150	50	50	50	50	50	50	
Placebo	20	20	20	20	20	20	50	50	50	50	50	50	

This schema specifies 6 baseline covariate strata for stratified sampling, for example 1 = U.S. Age 18-64 Minority; 2 = U.S. Age 18-64 non-Minority; 3 = U.S. Age  $\geq 65$  Minority;

 $4 = U.S \text{ Age} \ge 65 \text{ non-Minority}; 5 = \text{non-U.S. Age } 18-64; 6 = \text{non-U.S. Age} \ge 65.$ 

The vaccine group baseline negative strata are assigned large sample sizes because the correlates of risk analysis focuses on baseline negative vaccine recipients. The placebo group baseline negative strata are assigned small sample sizes given the expectation that almost all Day 57 bAb and nAb readouts

will be negative/zero given the absence of prior exposure to SARS-CoV-2 antigens. Equal stratum sizes are assigned for the vaccine and placebo groups in order to compare bAb and nAb responses in previously infected persons, studying potential differences in natural+vaccine-elicited responses vs. natural-elicited responses.

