If certain strata do not have enough eligible participants available for sampling, then additional sampling is done from other strata to keep the total immunogenicity subcohort sample size to close to 1620. A separate USG COVID-19 Response Team Antibody Marker sampling plan describes the algorithm, available upon request.

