We will also evaluate using a multivariate BIP that corresponds to all of these aforementioned candidate univariate BIPs, which may help to achieve the target  $R^2$  (see Table 10). When doing this, a separate BIP W will be used for each vaccine-induced immune response marker S(1). Let Y(a) be the counterfactual outcome of interest — e.g., a COVID disease endpoint by a prespecified time — if randomization assignment had been set to A = a. The analyses conducted will provide unbiased estimates of the estimands of interest when  $Y(a) \perp W|S(1)$  for  $a \in \{0, 1\}$ . The BIP W will be a learned function of baseline covariates L — that is, W = f(L) for a function f that will be learned based on the available data. All available baseline covariates will be considered for inclusion in L, including age, BMI, and Day 1 bAb or nAb to Nucleocapsid protein. If available, measurements of prior immune response to the vaccine vector (e.g., Day 1 bAb or nAb response to Ad26 for an Ad26 vector-based vaccine) will always be included in L.

If the trial of interest has more than 100 events on the vaccine arm in the subgroup of interest, then f will be chosen to be an estimate of the following population-level optimization problem:

minimize 
$$E[\{S - f(L)\}^2 | A = 1]$$
  
subject to  $f(L) \perp Y | A = 1, S$ .

The rationale for choosing f to (approximately) solve this optimization problem is that the BIP should be maximally predictive of S, while also satisfying the needed conditional independence assumption  $Y(a) \perp W|S(1)$  when a = 1. Moreover, the needed conditional independence assumption  $Y(a) \perp W|S(1)$ for the case that a = 0 is most plausible when this assumption is also satisfied for the case that a = 1. Also, because W = f(L) for some function f,  $Y(0) \perp W|S(1)$  is always more plausible than  $Y(a) \perp L|S(1)$ .

The solution to the above optimization problem is given by:

$$f(\ell) := \theta(\ell) - \frac{E[\theta(L)r(L)]}{E[r(L)^2]}r(\ell)$$

where  $\theta(\ell) := E\{S|A = 1, L = \ell\}, r(\ell) := \frac{m(\ell)}{E[m(L)]} - \frac{1-m(\ell)}{1-E[m(L)]}$  and  $m(\ell) := E[Y|A = 1, L = \ell]$ . The following strategy is used to estimate this solution:

- 1. Obtain an estimate  $\hat{\theta}$  of the function  $\theta$  by running a Superlearner of S against L in the vaccine arm, where inverse probability of sampling weights are used to account for two-phase sampling of the marker.

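### The 95% interval for the protective threshold s* ignores sampling error in the estimated antibody curve: coverage is close to nominal at VE 50–80%, but about 90% at VE 90% and 83% at VE 95% with 50 vaccine cases

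*Combined protocol and SAP*

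**What the plan says.** Section 18 covers every candidate marker: "For each antibody marker studied as a CoP, we will apply the Chang-Kohberger (2003) / Siber (2007) method". The threshold s* is the value at which 1 − P(S ≤ s*|A=1)/P(S ≤ s*|A=0) equals the estimated overall VE. The section then describes "calculating a 95% confidence interval for the threshold value" and locates its limits "as the points of intersection of the estimated RCDF curve with the 95% confidence interval for overall vaccine efficacy". It gives no confidence band for the reverse cumulative distribution function (RCDF), no bootstrap and no delta-method term.

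The RCDF is an estimate. Table 5 in Section 8.1 allots 150 baseline-negative vaccine recipients to each of six strata, with the explanation that "The vaccine group baseline negative strata are assigned large sample sizes because the correlates of risk analysis focuses on baseline negative vaccine recipients". Section 9.1.3 applies inverse-probability-of-sampling (IPS) weights when RCDF curves are estimated.

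Section 12.3.3 already defines a bootstrap that resamples inside and outside the subcohort within strata. Section 18 does not call on it.

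**The concern.** s* solves an equation with two estimated sides, VE and the marker distribution in vaccine recipients. Crossing the VE limits with a single fitted curve carries forward only the first error.

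For an effective vaccine, s* sits in the lower tail of the vaccine-arm distribution, at the 10th percentile when VE is 90%. The relative error of the estimated curve is large there. The omission matters more as cases accrue, because the VE error shrinks while the curve's error stays fixed by the subcohort size.

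Section 18 offers s* as a possible benchmark or study endpoint for future immunogenicity trials. An interval that is too narrow overstates how well that benchmark is known.

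**Working it through.** **Inputs from the documents**
- Subcohort vaccine recipients, baseline negative: 6 × 150 = 900 (Table 5; Section 24.4.1). Check of the table: 900 + 120 + 300 + 300 = 1,620, which agrees with the instruction to "keep the total immunogenicity subcohort sample size to close to 1620".
- Vaccine-arm cases d1: 50, from Table 4 (for example "CoP: Controlled VE 50"). Section 14 also foresees larger counts: "If the trial of interest has more than 100 events on the vaccine arm".
- VE: not fixed. Section 14 discusses 50–80% and 90% or higher; 0.90 is the default for simulated data in Section 24.3.1.
- Allocation 1:1: simulation default in Section 24.2.1.
- Placebo markers: expected below the detection limit (Section 15.3), so P(S ≤ s*|A=0) = 1.

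**Assumed:** the design effect from unequal weights. Stratum population sizes are not in the documents. Taking the appendix defaults for at-risk and minority status, a share aged 65 or over of 10–40%, and the same marker distribution in every stratum gives 1.28–1.67 (1.35 at a 25% share).

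**Formula.** Let F = 1 − VE. Then s* solves F1(s*) = F, and the plan's interval contains s* exactly when the estimated F1(s*) lies inside the confidence interval for 1 − VE. The shape of the marker distribution drops out. On the log scale:
- V1 = var(log RR) = 1/d1 + 1/d0, with d0 = d1/F
- V2 = var(log of estimated F1(s*)) = deff × (1 − F)/(900 × F)
- Coverage = 2Φ(1.96 × √[V1/(V1 + V2)]) − 1

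**Reproducing the stated 95%.** Setting V2 = 0 (curve known exactly) gives 95.0%. Simulation under that condition, with 40,000 replicates and an assumed 15,000 per arm, gave 95.0–95.3%. The label is right only if the curve has no error.

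**Interval as written, 50 vaccine cases, deff = 1**

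| VE | V1 | V2 | Coverage, formula | Coverage, simulated |
|---|---|---|---|---|
| 50% | 0.030 | 0.0011 | 94.6% | 94.6% |
| 70% | 0.026 | 0.0026 | 93.8% | 93.9% |
| 80% | 0.024 | 0.0044 | 92.8% | 93.0% |
| 90% | 0.022 | 0.0100 | 89.6% | 90.1% |
| 95% | 0.021 | 0.0211 | 83.4% | 84.2% |

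Worked line for VE 90%: V1 = 1/50 + 1/500 = 0.022; V2 = 0.9/(900 × 0.1) = 0.010; √(0.022/0.032) = 0.829; 1.96 × 0.829 = 1.625; coverage 89.6%.

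**Variations at VE 90%**
- deff 1.3: V2 = 0.013, coverage 88.0%. deff 1.7: V2 = 0.017, coverage 85.9%.
- 100 vaccine cases, deff 1: V1 = 0.011, coverage 84.4%.

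**If the VE interval comes from the primary analysis** ("typically approximately 150 in U.S. phase 3 studies"): vaccine cases = 150 × (1 − VE)/(2 − VE), which is 50 at VE 50%, 13.6 at VE 90% and 7.1 at VE 95%. With deff 1, coverage is 94.6%, 93.6% and 93.3%. With deff 2 it is 94.1%, 92.1% and 91.6%. The loss is therefore about 0.5 to 3.5 points.

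**With both errors included.** Using V1 + V2 restored simulated coverage to 95.0–95.6% for VE 50–95%, 25 to 100 vaccine cases and deff 1 or 1.35. A percentile bootstrap of both quantities was also checked with a simple random subcohort of 900 and 2,000 trials of 500 replicates each. It gave 94.5% (VE 70%, 50 cases), 94.7% (VE 90%, 50 cases), 94.2% (VE 90%, 100 cases) and 94.2% (VE 95%, 50 cases).

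**The case against.** The strongest reply is that the loss is usually small and nothing depends on it. Much of that stands.

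- **VE is not fixed.** A reader might infer that meeting the plan's conditions for correlate-of-protection analyses implies coverage of 84–90%. The documents do not support this. Tables 4 and 10 require at least 50 vaccine endpoints and, for some methods, feasibility checks; they set no VE. Over the moderate range that Section 14 plans for, coverage is 93–95%.
- **The design effect is assumed.** Reading 84% as the figure for VE 90% with 50 cases needs a design effect of 2, which nothing in the documents establishes. Nor is 84% a floor, since VE 95% or more cases gives lower values.
- **The event count is not stated.** Section 18 has no row in Table 4 or Table 10 and does not say which VE interval is used. With the primary-analysis interval the loss is small. Section 3.2, however, includes all blinded follow-up to the data lock in every correlate-of-protection analysis. At VE 90%, 150 events would give only about 14 vaccine cases, well short of 50.
- **Consequence.** The interval feeds no test, gate or decision. Section 18 presumes that the marker is already a correlate of protection and concedes that its assumptions are highly simplified. That concession concerns perfect protection above s* and zero efficacy below it. It does not cover sampling error and does not justify the 95% label.

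**Conclusion.** The interval is wrong as written. It omits the sampling error of the RCDF, and no other section supplies it. The resulting error is one-sided, towards under-coverage.

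With 50 vaccine cases, 1:1 arms and no design effect, the shortfall is minor at VE 50–80% (0.4 to 2.2 points), about 5 points at VE 90% and about 12 at VE 95%. Unequal weights or further cases make it worse; a VE interval based on about 150 events makes it small.

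The direction and the omission are certain. The size rests on VE, on which event count supplies the VE interval, and on a design effect that cannot be derived from the documents. Severity is modest, because s* is complementary information without a decision rule.

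**What to change.** In Section 18, replace the intersection rule with an interval that carries both errors. In each replicate of the stratified bootstrap of Section 12.3.3, applied in both arms, re-estimate VE and the IPS-weighted marker distribution, solve for s*, and take the 2.5th and 97.5th percentiles. Alternatively, add the variance of the log estimated distribution function to the variance of log(1 − VE) before inverting. State also which follow-up supplies the VE estimate and its interval.

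The cost is a sentence or two in the SAP and a short addition to existing code. The interval becomes wider: on the log-F scale with 50 cases at VE 90%, by √(0.032/0.022) = 1.21 times. The point estimate of s* does not change.
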